- 8. All participants will be asked to return for an EOT visit. For participants who prematurely discontinue study treatment, the EOT visit will occur within 5 days of the last intake of study treatment. For participants who complete the treatment period as planned, the Week 12 visit corresponds to the EOT visit.
- 9. During unscheduled visits, additional assessments may be performed at the discretion of the investigator. The assessments in brackets are recommended to be performed on an unscheduled visit, based on medical judgment.

10. Stanford Sleepiness Scale to be filled in for the first 2 weeks of study treatment, twice daily, at breakfast (before morning dose) and around midday, prior to lunch time.

AE = adverse event; BP = blood pressure; BWSQ = Benzodiazepine Withdrawal Symptom Questionnaire; CGI-C = Clinical Global Impression of Change scale; CGI-S = Clinical Global Impression of Severity scale; C-SSRS© = Columbia Suicide Severity Rating Scale©; eCRF = electronic Case Report Form; ECG = electrocardiogram; EDE-Q: Eating Disorder Examination Questionnaire; EOS = End-of-Study; EOT = End-of-Treatment; HAMD-17 = Hamilton Rating Scale for Depression (17-item); ICF = informed consent form; IMP = Investigational Medicinal Product; IRT = Interactive Response Technology; MINI© = Mini International Neuropsychiatric Interview©; NA = not applicable; PGI-C = Patient Global Impression of Change scale ; PGI-S = Patient Global Impression of Severity scale; PK = pharmacokinetic(s); PR = pulse rate; RR = respiratory rate; SAE = serious adverse event; SCID-5 = Structured Clinical Interview for DSM-5; To = temperature; U1 = unscheduled visit; V = visit; WOCBP = women of childbearing potential; YBOCS-BE = Yale-Brown Obsessive-Compulsive Scale Modified for Binge Eating.

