# ACT-539313 Binge Eating Disorder Protocol ID-082A201 Final Version 3 4 May 2021, page 37/140

#### Confidential

Objectives	Corresponding endpoints
Objectives	Corresponding endpoints
To assess treatment effect on anxiety and depressive	• Change from baseline to Week 6 and to Week 12 in the HAMD-17 total score.
symptoms	• Change from baseline to Week 6 and to Week 12 in the HAMD-17 subitems 10 and 11.
	• Change from baseline to Week 6 and to Week 12 in the HAMD-17 MPS score.
To assess treatment effect on attitudinal and behavioral dimensions of eating and	• Change from baseline to Week 12 in the EDE-Q7 global score and 3 subscales scores (dietary restraint, shape/weight overvaluation and body dissatisfaction).
overall symptomatology in	• CGI-C score at Week 12.
BED	• PGI-C score at Week 12.
	• Change from baseline to Week 12 in the CGI-S.
	• Change from baseline to Week 12 in the PGI-S.
To access treatment offect on	Change from begaling to Weelt 12 in body weight
hody weight and glucose	• Change from baseline to week 12 in body weight.
levels	• Change from baseline to week 12 in HbA1c.
Safety objectives	
To assess the safety of ACT-539313 in patients with BED	• TEAEs a defined as an AE occurring from the start of study treatment administration up to the EOS.
	• Treatment-emergent SAEs defined as an SAE occurring from the start of study treatment administration up to the EOS.
	• TEAEs a leading to premature discontinuation of the study treatment.
	• Treatment-emergent AESIs up to EOS. AESIs include AEs related to somnolence (defined by pre-specified terms) from the start of study treatment administration up to the EOS.
	• Occurrence of daytime sleepiness assessed by SSS from the start of study treatment administration up to Visit 4 (Week 2).

Objectives	Corresponding endpoints		
	• Treatment-emergent marked laboratory abnormalities b from the start of study treatment administration to all assessed time points during the study.		
	• Change in vital signs (systolic and diastolic blood pressure, temperature, respiratory rate, and pulse rate) from baseline to all assessed time points during the study.		
	• Medically relevant ECG abnormalities b while on study treatment from baseline to all assessed time points during the study.		
	• Occurrence of withdrawal symptoms upon treatment discontinuation, as measured by change between Week 12 / EOT and EOS visit in BWSQ total score and HAMD-17 total score.		

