#### 5.9.1 Study treatment premature discontinuation

The decision to prematurely discontinue study treatment may be made by the study participant, the investigator/delegate, or the sponsor personnel.

The investigator/delegate has the option of prematurely discontinuing study treatment for a given study participant in response to an AE, a diagnostic or therapeutic procedure, a laboratory abnormality, or for administrative reasons. If study treatment is interrupted by the study participant for any reason, she/he must inform the investigator/delegate as soon as possible. Study treatment dose interruptions must be recorded in the eCRF.

The investigator/delegate must permanently discontinue study treatment for a given study participant if, on balance, he/she believes that continued administration would be contrary to the best interests of the study participant.

Study-specific criteria for permanent discontinuation of study treatment are described in Sections 5.9.1.1 to 5.9.1.4.

The main reason for permanent discontinuation of study treatment (e.g., due to pre-specified study treatment discontinuation criteria, an AE, lack of efficacy, study termination) must be documented in the eCRF.

A study participant who prematurely discontinues study treatment is not considered as withdrawn from the study.

The study participant who prematurely discontinues study treatment or who is permanently discontinued from study treatment will be asked to return for an EOT visit within 1 to 5 days of last intake of study treatment and thereafter to attend follow-up visits as defined in the schedule of activities [Table 1, Section 7.2].

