7.7 Withdrawal symptoms

7.7.1 Benzodiazepine Withdrawal Symptoms Questionnaire

The BWSQ consists of 20 items with each item rated by the subject as either 0 (No), 1 (Yes-moderate), or 2 (Yes-severe). The change in BWSQ Total score (possible range: 0 to 40) from the last available assessment during the treatment period to EOS will be summarized. Observed values will also be summarized.

The number (%) of study participants with a BWSQ Total score above 20 will be tabulated by visit (EOT and EOS).

The number (%) of study participants with one or more BWSQ symptom scored as 'severe' will be tabulated by visit (EOT and EOS).

In addition, withdrawal symptoms after study treatment discontinuation will be assessed through the incidence of AEs occurring during the safety follow-up period. As described in the respective section [Section 7.2], the incidence of AEs occurring during the safety follow-up period will be summarized.

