11.2 Study periods

The Screening period is defined as the time from the informed consent date until one day before the study treatment start date, or date of screening failure.

The treatment period is defined as the time from the day of study treatment start until the day of EOT (Week 12), or, for those who prematurely discontinued study treatment (i.e., those without an EOT date), until the day of study treatment end date. In case of missing

ACT-539313		Statistical Analysis Plan
ID-082A201	Confidential	for Clinical Study Report
1 April 2022, page 40/60	Confidential	Version 3
		Doc No D-22.100

study treatment end date, EOT will be imputed using the last available visit/assessment date.

The safety follow-up period is defined as the time from one day after EOT until EOS date.

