11.5 Change from baseline

The change from baseline is defined as the post-baseline value (any assessment performed after baseline and up to EOS) minus the baseline value. A positive number indicates an increase as compared to baseline.

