For the calculation of SSS, study days falling in the time window 2-15 will be considered for the analyses since study day 1 corresponds to assessments done on the day of the randomization where information on the SSS should not be collected.

11.8 Time window definitions for calculating exploratory efficacy and safety endpoints collected during site visits

The exploratory efficacy endpoints YBOCS-BE, PGI-S, CGI-S, PGI-C, CGI-C, EDE-Q, and HAMD-17 are collected during specific site visits [Table 7].

The safety endpoint C-SSRS[©] is collected during all site visits [Table 8].

For both efficacy and safety endpoints, if more than one assessment falls within the same time window, the assessment which is performed closest to the target study day will be considered for the analysis.

Table 7Time windows (in days) for visit-based exploratory efficacy
endpoints: YBOCS-BE, PGI-S, CGI-S, PGI-C, CGI-C, EDE-Q,
HAMD-17

Week	Target study day	Window	Endpoint
Baseline	1	1–1	YBOCS-BE, PGI-S, CGI-S, EDE-Q, HAMD-17
1	8	2-14	CGI-C, PGI-C
4	29	22-36	YBOCS-BE, PGI-S, CGI-S, PGI-C, CGI-C, EDE-Q
6	43	37–49	HAMD-17
8	57	50–64	YBOCS-BE, PGI-S, CGI-S, PGI-C, CGI-C, EDE-Q
12	85	78–92	YBOCS-BE, PGI-S, CGI-S, PGI-C, CGI-C, EDE-Q, HAMD-

CGI-C = Clinical Global Impression of Change scale; CGI-S = Clinical Global Impression of Severity scale; EDE-Q = Eating Disorder Examination Questionnaire; HAMD-17 = Hamilton Rating Scale for Depression (17-item); PGI-C = Patient Global Impression of Change scale; PGI-S = Patient Global Impression of Severity scale; YBOCS-BE = Yale-Brown Obsessive-Compulsive Scale modified for Binge Eating.

Table 8Time windows (in days) for C-SSRS©

Week	Target study day	Window	
Baseline	1	1–1	
1	8	5-11	
2	15	12–18	
4	29	22–36	
6	43	37–49	
8	57	50–64	
10	71	65–77	
12	85 78–92		

C-SSRS[©] = Columbia-Suicide Severity Rating Scale[©]

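### For participants who stop treatment early, the SAP's period rule leaves the BWSQ withdrawal change without a start value and moves the HAMD-17 start back to Week 6 or baseline, unlike the protocol's EOT-to-EOS change

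*SAP*

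**What the plan says.** **Protocol.** Section 5.9.1 says that a participant who stops early "will be asked to return for an EOT visit within 1 to 5 days of last intake of study treatment". Footnote 8 of Table 1 has a looser form: "For participants who prematurely discontinue study treatment, the EOT visit will occur within 5 days of the last intake of study treatment". EOS follows 10 ± 3 days after EOT. Section 7.2.5.6 schedules the BWSQ at EOT and EOS only. Section 7.2.4.8 schedules the HAMD-17 at screening, randomization, Week 6, EOT and EOS. Table 2 defines the withdrawal endpoint "as measured by change between Week 12 / EOT and EOS visit in BWSQ total score", treats HAMD-17 likewise, and is echoed in Section 9.2.10 with the same start and end.

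**SAP, withdrawal change.** Section 7.7.1 takes the BWSQ change "from the last available assessment during the treatment period to EOS will be summarized", and Section 7.7.2 uses the same rule for HAMD-17. Section 11.2 normally closes the treatment period at Week 12 EOT. Its exception reads: "for those who prematurely discontinued study treatment (i.e., those without an EOT date), until the day of study treatment end date". Later in the same section comes this definition: "The safety follow-up period is defined as the time from one day after EOT until EOS date". Section 12.1 lists only a change to the demographics analyses, and Sections 12.2 to 12.4 are marked not applicable.

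**SAP, efficacy windows.** Table 7 assigns HAMD-17 records to Week 6 (days 37–49, target 43) and Week 12 (days 78–92, target 85). Section 11.8 adds that "if more than one assessment falls within the same time window, the assessment which is performed closest to the target study day" is used. Section 11.5 defines a post-baseline value as "any assessment performed after baseline and up to EOS".

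**The concern.** Withdrawal symptoms on stopping the drug are a named safety endpoint, and people who stop early are part of the group it concerns. If the SAP's start point does not exist for them, the BWSQ change describes completers only and no table will say so. For HAMD-17 a number is still produced, but it means something else: a change from Week 6 or Day 1 to EOS mixes the course of symptoms on treatment with any effect of stopping.

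The second issue is smaller. Nothing in Table 7 or Section 11.5 requires a HAMD-17 record to have been made on treatment. A score taken days after the last dose can therefore be analysed as a Week 6 or Week 12 efficacy value.

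**Working it through.** **1. Visit timings.** The protocol's maximum participation of 128 days is reproduced by 28 screening days + latest EOT day (85 + 2 = 87) + 13 days to EOS = 128. The timings used below are therefore the protocol's own.

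**2. BWSQ start value.** Let L be the last-dose day, e the lag to the premature EOT visit (1 to 5 days) and s the lag from EOT to EOS (7 to 13 days).
- The SAP treatment period ends on day L.
- The EOT visit is on day L + e, and L + e ≤ L is impossible for e ≥ 1. No BWSQ lies inside the treatment period.
- If EOT in the follow-up definition means the visit, follow-up starts on day L + e + 1. The EOT visit then belongs to neither period.
- EOS is on day L + e + s, which is 1 + 7 = 8 to 5 + 13 = 18 days off drug.

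Under the protocol's definition, every discontinuer who attends both visits has a change over 7 to 13 days.

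**3. HAMD-17 start value.** The last record on or before day L is Week 6 if Visit 6 preceded the stop, and otherwise Day 1.

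**4. HAMD-17 in the Table 7 windows.** Last-dose days that allow an off-drug record:
- EOT visit in Week 6: 37 − 5 = 32 to 49 − 1 = 48.
- EOT visit in Week 12: from 78 − 5 = 73.
- EOS in Week 6: 37 − 18 = 19 to 49 − 8 = 41.
- EOS in Week 12: from 78 − 18 = 60.

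**5. Illustrative shares.** Assumptions: L is uniform, all lags are equally likely, Visit 6 falls on days 41–45 if still on treatment, every visit is attended, and the record closest to target is used. L runs either to day 77 (the day before the Week 12 window opens) or to day 82 (the day before the earliest scheduled Week 12 visit, 85 − 2 = 83).

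| Records admitted | Last dose, days | Off-drug Week 6 | Off-drug Week 12 |
|---|---|---|---|
| Premature EOT and EOS | 1–77 | 25.0% | 16.9% |
| Premature EOT and EOS | 1–82 | 23.5% | 22.0% |
| Premature EOT only | 1–77 | 12.0% | 3.9% |
| Premature EOT only | 1–82 | 11.3% | 9.8% |

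Hand check of one cell: for L to 77, the pairs (L, e) with L + e ≥ 78 number 1 + 2 + 3 + 4 + 5 = 15 out of 77 × 5 = 385, or 3.9%. For L to 82 they number 15 + 5 × 5 = 40 out of 410, or 9.8%.

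**6. Completers.** EOT is within 2 days of day 85. EOS falls on days 83 + 7 = 90 to 87 + 13 = 100, at least 5 days from target, so the EOT record is always chosen when it is present.

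**The case against.** **The bracket in Section 11.2 could mean only discontinuers who skipped the EOT visit.** Attenders would then keep EOT inside the treatment period and their BWSQ change would be defined. Section 7.7.1 also tabulates BWSQ at EOT and EOS without excluding discontinuers, so its author evidently expected those data. This is a fair account of the likely intent. But the bracket is introduced as an equivalence, which makes every discontinuer someone without an EOT date, and a programmer following it would drop the start value. Footnote 8's looser wording could also allow a same-day EOT visit, which would escape the problem. Table 1 and Section 5.9.1 both say 1 to 5 days.

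**A reader might infer that withdrawal information on early stoppers is lost altogether.** It is not. Observed BWSQ values, counts above 20 and counts of severe symptoms are still reported by visit, as are adverse events in follow-up. Only the change score fails.

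**EOS may never have been meant to enter Table 7.** The model names Week 6 (Visit 6) and Week 12 (EOT), the table is headed as visit-based, and for the C-SSRS Section 7.8 assigns EOS to follow-up. That EOS records enter is an inference, so the shares are shown both ways. The premature EOT record remains exposed on either view.

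**A reader might also infer that using off-drug HAMD-17 scores breaches the hypothetical strategy.** The documents do not support that. The strategy is written for BE days and BE episodes only. HAMD-17 has no estimand, and its analysis is exploratory and descriptive.

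**A pre-stop start value is defensible for measuring withdrawal.** It is, for HAMD-17. BWSQ has no pre-stop value, and the protocol fixed EOT as the start for both scales.

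**Conclusion.** The main point stands. As written, the SAP does not compute the protocol's EOT-to-EOS withdrawal change for participants who stop early. The BWSQ change has no start value and the HAMD-17 change has a different one, and the departure is not declared. Section 11.2's statement that discontinuers lack an EOT date contradicts the protocol.

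The number losing a BWSQ change is at most the number of discontinuers who attend both EOT and EOS. If 20% discontinued (an assumption; the protocol's 20% refers to missing Week 11–12 data), the ceiling would be 0.20 × 120 = 24. A reader might take the 9 site-closure participants in the SAP appendix as a minimum, but nothing shows that they attended both visits.

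The window gap is secondary. Under the uniform-stopping assumptions, about 24–25% of discontinuers would get an off-drug Week 6 value and 17–22% an off-drug Week 12 value if EOS records are admitted. If only premature EOT records are, the figures are about 11–12% and 4–10%. The affected analyses are a descriptive safety summary and an exploratory model. The primary endpoint and completers with an EOT visit are untouched.

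**What to change.** - **SAP 7.7.1 and 7.7.2:** compute the change from the EOT-visit assessment (Week 12 or premature EOT) to EOS, as in protocol Table 2 and Section 9.2.10. Showing premature EOT separately would help, because those start values are already 1 to 5 days off drug.
- **SAP 11.2:** correct the description of discontinuers as lacking an EOT date, and say which period a premature EOT visit belongs to. Putting the start point in Section 7.7 avoids having to lengthen the treatment period, which would also alter the adverse-event tables by period.
- **SAP 11.8:** state that EOS records never enter the Table 7 efficacy windows and that discontinuers' records after the treatment end date are excluded. This aligns HAMD-17 with the approach written for BE days and BE episodes.
- If the sponsor prefers the current start point for HAMD-17, declare it in SAP 12.1 as a change from the protocol.

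Cost: a few sentences and small programming changes, with no new data or visits.

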7.7.2 Hamilton Depression Rating Scale

The change in HAMD-17 Total score from the last available assessment during the treatment period to EOS will be summarized. Observed values will also be summarized.

7.8 Columbia-Suicide Severity Rating Scale[©]

The C-SSRS[©] is an instrument that evaluates suicidal ideation and behaviors.

The C-SSRS[©] outcome categories are provided below. Each category has a binary response (yes/no).

ACT-539313		Statistical Analysis Plan
ID-082A201	Confidential	for Clinical Study Report
1 April 2022, page 37/60	Confidential	Version 3
		Doc No D-22.100

- 1 Wish to be dead
- 2 Non-specific active suicidal thoughts
- 3 Active suicidal ideation with any methods (not plan) without intent to act
- 4 Active suicidal ideation with some intent to act, without specific plan
- 5 Active suicidal ideation with specific plan and intent
- 6 Preparatory acts or behavior
- 7 Aborted attempt
- 8 Interrupted attempt
- 9 Actual attempt (non-fatal)
- 10 Completed suicide

Categories 1-5 relate to suicidal ideation and a score of 0 is assigned if no suicidal ideation is present. Categories 6-10 relate to suicidal behavior.

Self-injurious behavior without suicidal intent is also a C-SSRS[©] outcome (although not suicide-related) and has a binary response (yes/no).

Based on the C-SSRS[©], the number (%) of study participants with suicidal ideation by category, suicidal behavior by category, suicidal ideation or suicidal behavior, and/or self-injurious behavior without suicidal intent, during the treatment period and the safety follow-up period will be tabulated. Percentages will be based on the number of study participants with at least one post-baseline C-SSRS[©] assessment. The assessments done at Week 1, 2, 4, 6, 8, 10, 12 will be assigned to the treatment period while the assessment done at EOS will be assigned to the safety follow-up period.

Shift from baseline showing any change in suicidal ideation and suicidal behavior during the treatment period and the safety follow-up period will be provided. Study participants will be summarized under the worst of the following three categories, shown here in the order from best to worst: 1) No suicidal ideation or behavior, 2) Suicidal ideation, and 3) Suicidal behavior (study participants with both suicidal ideation and suicidal behavior are also included in the suicidal behavior category).

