# 5.9.2 Withdrawal from the study

Study participants may voluntarily withdraw from the study without justification for any reason at any time. Study participants are considered withdrawn if they state an intention to withdraw further participation in all components of the study (i.e., withdrawal of consent), die, or are lost to follow-up [see Section 5.9.3]. If a study participant withdraws consent for further study participation, no further data will be collected in the eCRF from the date of withdrawal onward. The investigator/delegate may withdraw a study participant from the study (without regard to the study participant's consent) if, on balance, he/she believes that continued participation in the study would be contrary to the best interests of

the study participant. Withdrawal from the study may also result from a decision by the sponsor for any reason, including premature termination or suspension of the study [see Section 10.10].

Enrolled study participants who prematurely discontinue from the study for any reason will not be replaced.

If, for whatever reason (except death or loss-to-follow-up), a study participant is withdrawn from the study, the investigator/delegate should make best efforts to schedule a last appointment / telephone call to assess the safety and well-being of the study participant, collect unused study treatment and discuss follow-up medical care. Data obtained during this last appointment / telephone call will be recorded in the study participant's medical records, but they will not be collected in the eCRF.

The main reason for premature withdrawal from the study must be documented in the eCRF.

The investigator must provide follow-up medical care for all study participants who are prematurely withdrawn from the study, or must refer them for appropriate ongoing care, as described in Section 6.3.

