#### 6.1.3 Treatment assignment

A total of approximately 120 study participants will be randomized in a 1:1 ratio to ACT-539313 or placebo. Randomization will not be stratified.

After verifying that the study participant meets all inclusion criteria and none of the exclusion criteria, the investigator/delegate contacts the IRT system at Visit 2 to randomize the study participant. The IRT assigns a randomization number to the study participant and assigns the treatment kit number, which matches the treatment arm assigned by the randomization list to the randomization number.

The IRT system is handled by an external independent vendor who will generate the randomization list.

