# 9.2.10 Specific safety endpoints

*Daytime sleepiness* is defined daily as any score > 3 on the SSS after taking the morning dose. It will be collected on Days 1–14 and expressed as a number of days per week (as for the primary efficacy outcome). A minimum of 7 diary entries are required, otherwise the data will be considered missing. The mean number of days with daytime sleepiness per week will be summarized by treatment group.

The number (%) of study participants with *suicidal ideation and/or behavior* based on the C-SSRS© will be tabulated by visit and treatment group.

*Withdrawal effects* will be described summarizing changes from changes from Week 12/EOT to EOS in BWSQ and HAMD-17 by treatment group.

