#### 9.4 Sample size

The sample size is based on the primary efficacy endpoint, change from baseline to Week 12 in the number of BE days per week.

In 2 studies using lisdexamfetamine in study participants with BED [McElroy 2016] the difference between lisdexamfetamine and placebo for this endpoint was -1.35 (SD = 1.6) and -1.66 (SD = 1.6) days per week. The corresponding effect size was 0.83 (95% CI: 0.60–1.05) and 0.97 (95% CI: 0.72–1.21), respectively. In the USA, lisdexamfetamine is categorized as a Schedule II medication. For this reason, a smaller effect size by ACT-539313 may still be considered clinically important if it has a better safety profile than lisdexamfetamine.

In an earlier study comparing topiramate to placebo in study participants with BED [McElroy 2007] the difference in the means of the changes from Baseline to Week 16 between topiramate and placebo was -1.0 with a common SD of 2.0, providing an effect size of 0.5 (95% CI: 0.3–0.7).

In a recent study with dasotraline, the LSmean reduction from Baseline in number of BE days per week was significantly greater for dasotraline vs placebo at Week 12 (-3.74 vs -2.75), for an effect size = 0.74 [McElroy 2020].

Based on the above, it is assumed that a treatment group difference of 1 BE day per week (corresponding to an effect size of 0.5 to 0.7, depending on the SD) is clinically meaningful.

The sample size is based on the power to detect a reduction of at least 1 BE day per week at Week 12 (with an SD of 1.6, this corresponds to an effect size of 0.65), between ACT-539313 and placebo, at a significance level of 5% two sided. Table 5 shows the sample size needed to detect a difference between placebo and ACT-539313 for different effect sizes.

	-	-		
Effect size	0.5	0.6	0.7	
Power				
90%	170	118	86	
80%	126	88	66	

Table 5Total sample size for 90% power

For a two-sided  $\alpha = 0.05$  and 1:1 randomization

The sample sizes reported in Table 5 are based on a t-test, but are also valid for a mixed model for repeated measures, retaining close to 90% (or 80%) power in the case of missing Week 11–12 data (up to 20%).

Table 6 shows the power to detect a difference between placebo and ACT-539313 for a sample size of 100–120 study participants.

Table 6Power for sample sizes of 100 and 120

Effect size	0.5	0.6	0.7
Sample size			
100	71%	85%	94%
120	78%	91%	97%

For a two-sided  $\alpha = 0.05$  and 1:1 randomization

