7.3 Laboratory tests

Laboratory analyses are based on data received from the central laboratory. Laboratory data will be converted into SI units. Unless noted otherwise, summaries and listings will include scheduled, re-test, and unscheduled assessments.

Descriptive summary statistics for each scheduled visit (re-test excluded) will be provided for observed values and change from baseline in both hematology and blood chemistry laboratory parameters.

The main laboratory parameters will be displayed graphically using boxplots considering only scheduled visit (re-test and unscheduled assessments excluded) and will be grouped (i.e., shown in the same panel) as follows:

- Hemoglobin, hematocrit, platelets, leukocytes (white blood cell count)
- Glucose, uric acid, cholesterol, triglycerides
- Total bilirubin, ALT, AST
- ALP, GGT

Marked laboratory abnormalities are defined in the appendix [Section 14.14]. The number (%) of participants with treatment-emergent marked laboratory abnormalities will be tabulated. A subject will be counted only once but may be reported in more than one marked laboratory abnormality criterion of a given parameter. Percentages will be based on the number of participants having at least one post-baseline value for a given parameter.

Shift from baseline to worst value post-baseline based on laboratory normal ranges will be provided for the following laboratory parameters:

- Liver enzymes: ALT, AST, GGT and BILI.
- Lipids: total cholesterol and triglycerides.
- Hematology: hemoglobin, hematocrit, platelets, leukocytes (absolute count), neutrophils (absolute count), lymphocytes (absolute count).

All laboratory data for participants with at least one marked laboratory abnormality during the treatment period will be listed. Any local laboratory data collected will be listed separately.

ACT-539313		Statistical Analysis Plan
ID-082A201	Confidential	for Clinical Study Report
1 April 2022, page 34/60		Version 3
		Doc No D-22 100

Elevated liver parameters during the treatment period will be summarized: the number (%) of study participants meeting the criteria defined below within a given central laboratory sample will be tabulated by treatment group. Percentages will be based on the number of study participants having at least one post-baseline value for all parameters listed below.

- AST or ALT $> 3 \times ULN$
- AST or ALT $> 5 \times ULN$
- AST or ALT $> 10 \times ULN$
- BILI > $2 \times ULN$
- ALP > $1.5 \times ULN$

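### C-SSRS percentages for the safety follow-up period should rest on participants assessed at EOS, not on everyone with any post-baseline form

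*SAP*

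**What the plan says.** SAP 7.8 states that the number and percentage of participants with each C-SSRS outcome "during the treatment period and the safety follow-up period will be tabulated". The denominator follows directly: "Percentages will be based on the number of study participants with at least one post-baseline" C-SSRS assessment. The next sentence allocates forms to periods: Weeks 1 to 12 go to treatment, and "the assessment done at EOS will be assigned to the safety follow-up period". The SAP does not limit the denominator to participants assessed in the period concerned. It specifies no row for participants not assessed, and the shift tables have three outcome categories with none for missing.

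Protocol 9.2.10 planned this output differently: participants with suicidal ideation or behavior "will be tabulated by visit and treatment group". It names no denominator. SAP 12.1 does not list the move from visits to periods among its changes.

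Protocol 7.2.5.7 says that each C-SSRS after screening covers the time since the preceding visit. Protocol Table 1 schedules the scale at every visit, including EOS.

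**The concern.** Numerator and denominator do not match for follow-up. Only an EOS form can place someone in the numerator, yet any post-baseline form places them in the denominator. Since each form looks back only to the visit before it, on-treatment forms say nothing about the time after End-of-Treatment (EOT). A participant without an EOS form is unobserved in follow-up but is treated as free of suicidality.

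Missing EOS forms are foreseeable. After withdrawal of consent, "no further data will be collected in the eCRF from the date of withdrawal onward" (Protocol 5.9.2), and Protocol 5.9.3 provides for loss to follow-up.

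At stake is the readability of a declared safety endpoint: the C-SSRS is followed up to EOS (Protocol Table 2), and follow-up is where suicidality after stopping the drug would appear. The percentage would be pulled towards zero by missing forms. If more forms are missing in one arm than in the other, part of any difference between arms would reflect attendance.

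**Working it through.** The documents give no C-SSRS rate, no denominator count and no EOS missingness, so there is no stated figure to reproduce. The check is one of dilution.

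**Inputs**

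- Planned size, Protocol 6.1.3: "A total of approximately 120 study participants will be randomized in a 1:1 ratio", so 120/2 = 60 per arm.
- N_any, participants with any post-baseline form: taken as 60 per arm (assumption).
- N_EOS, participants with an EOS form: not given. Assumed 5% to 20% missing. The only missing-data fraction in the documents is the allowance of up to 20% for Week 11–12 data in Protocol 9.4. That concerns the diary endpoint and serves here only to set the range.
- x, participants with an event on the EOS form: 2 (illustration).

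**Formulas**

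- SAP percentage for follow-up = x / N_any
- Rate among EOS-assessed participants = x / N_EOS
- Ratio of the first to the second = N_EOS / N_any
- Relative understatement = 1 − N_EOS / N_any

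An EOS form is itself post-baseline, so N_EOS cannot exceed N_any. The SAP percentage can never be above the EOS-assessed rate, and it is below it whenever a form is missing and x is at least 1.

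**Results for x = 2, N_any = 60**

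| EOS forms missing (assumed) | N_EOS | SAP rule | EOS-assessed | Ratio |
|---|---|---|---|---|
| 5% | 57 | 2/60 = 3.33% | 2/57 = 3.51% | 0.95 |
| 10% | 54 | 3.33% | 2/54 = 3.70% | 0.90 |
| 15% | 51 | 3.33% | 2/51 = 3.92% | 0.85 |
| 20% | 48 | 3.33% | 2/48 = 4.17% | 0.80 |

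The absolute gap runs from 3.51 − 3.33 = 0.18 to 4.17 − 3.33 = 0.84 percentage points.

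**Unequal attendance (wholly hypothetical).** Suppose both arms have a 5% rate among those assessed, with 20% of EOS forms missing on ACT-539313 and 5% on placebo. The table would show 5% × 48/60 = 4.00% against 5% × 57/60 = 4.75%, a ratio of 4.00/4.75 = 0.84 where the assessed rates are equal. Swapping the arms reverses the direction.

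**The case against.** The strongest defence is that a fixed denominator is a recognised descriptive choice that the SAP uses elsewhere. For laboratory abnormalities, "Percentages will be based on the number of participants having at least one post-baseline value for a given parameter" (SAP 7.3), which is a restriction by parameter and not by period; the elevated-liver summary for the treatment period also uses participants with post-baseline values; and follow-up adverse events (SAP 7.2) have no period-specific denominator. The laboratory precedent is weak. Protocol Table 1 schedules no laboratory sample at EOS, so, unscheduled samples aside, post-baseline there already means the treatment period. For the C-SSRS it does not.

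A second defence is that the sentence might describe one table pooled over both periods, for which the denominator would fit. Allocating visits to periods would then serve little purpose, and if both readings are open the programmer needs the clarification anyway.

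Several points against a larger claim do stand:

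- A reader might infer that people never assessed are counted as free of suicidality. Anyone without a post-baseline form is already excluded; those affected were assessed on treatment but not at EOS.
- A reader might take x/N_EOS as the true follow-up risk. It is the rate among those who attended, and equals the underlying risk only if absence is unrelated to suicidality.
- A reader might assume that every early stopper lacks an EOS form. Protocol 5.9.1 keeps participants who stop treatment in the study and asks them to attend follow-up. SAP 14.4 counts 9 participants who stopped because of site closure, but SAP 1 says that participants at those sites finished the study, so some may have EOS forms.
- The mirror error in the treatment-period percentage needs someone whose only post-baseline form is the EOS one. With seven scheduled treatment-period assessments, that is improbable.
- The signal is not hidden. Counts accompany the percentages, all safety data are listed (SAP 7.1), and study discontinuation is tabulated by arm (SAP 5.1.3). No test or stopping rule uses this percentage.

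**Conclusion.** The mismatch is in the text of SAP 7.8, and nothing elsewhere in either document corrects it. The follow-up percentage is the EOS-assessed rate scaled by N_EOS/N_any. Under the assumed 5% to 20% of missing EOS forms, it is understated by 5% to 20% in relative terms, or 0.2 to 0.8 percentage points for 2 events in 60. With complete EOS forms, or with no events, the effect is zero.

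The documents do not support the inference that a suicidality signal is concealed or that the arms will be miscompared. They give neither EOS attendance nor event rates by arm, so distortion of the comparison is a possibility that depends on unequal attendance. The SAP also states no percentage denominator for the shift tables, so no error is shown there, only the absence of a rule.

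This is a minor correction to a descriptive safety table. No efficacy result or hypothesis test is touched.

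**What to change.** In SAP 7.8, replace the denominator sentence with wording such as: *For each period, the denominator is the participants who have at least one C-SSRS assessment assigned to that period (for safety follow-up, the EOS assessment).* Print that n in the table with the number not assessed in the period, by arm. Use the same participants in the period-specific shift tables.

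The cost is one sentence and one added table row; no data collection, design or inference changes. The downside is that the follow-up figure becomes an observed-case rate among EOS attenders, which can itself mislead if absence is related to suicidality. The not-assessed count should therefore stand beside it, so that a reader can judge how much of the period went unobserved in each arm.
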